In addition to consent for study participation, subjects will be asked to provide consent to coordinate care and share clinical data with/from the ARMS program, including review of medical records (e.g., routine ARMS clinical evaluation) to confirm inclusion/exclusion criteria, extract relevant clinical data obtained during the routine ARMS clinical evaluation from the medical record (e.g. diagnoses, treatment history, family history of substance use), track treatment engagement at ARMS, and facilitate good clinical care during the study. Subjects who are unable or unwilling to provide such consent will not be eligible for further participation. Subjects will also be asked to provide consent for audio-recording of group treatment sessions. The purpose of audio-recording, measuring therapist adherence to the treatment protocol, will be explained. Subjects who decline consent to audio-record their sessions will not be enrolled in the study. On the consent form, subjects will also be asked to list their preferred methods of communication between sessions (regarding scheduling and other logistical issues) and will be presented with pertinent information about the risks of the various methods of communication. Participants will be asked to provide consent to be contacted via e-mail and/or text messaging over the course of the study for scheduling purposes and appointment reminders.

V. STUDY PROCEDURES

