UP + TAU condition: After randomization, participants randomized to the UP + TAU condition will undergo TAU at ARMS and be offered 16 additional, twice-weekly group UP sessions, also at ARMS (see *Intervention*). Participants in the UP + TAU condition will undergo the same midand post-treatment assessments as the TAU condition, plus the CSQ-8 and a semi-structured interview to collect feedback about the intervention (see *Measures*). The mid-treatment assessment will occur after each participant's 8th UP session OR between 4-6 weeks after randomization, and the post-treatment assessment will occur within two weeks after each participant's 16th UP session. The same risk assessment procedures for mid- and post-treatment assessments used in the TAU condition will also apply to the UP + TAU condition. Should a UP + TAU participant condition have two consecutive unplanned absences from a UP group session, up to three attempts to contact will be made regarding their absence. There will not be a maximum number of missed UP sessions warranting a participant to step out of the 16-session group protocol. After completing the post-treatment assessment, their participation in the study will be complete.

Group UP sessions will take place at the ARMS program at MGH. Study assessment visits (screening/baseline, mid-treatment, and post-treatment) may take place at the ARMS program, the Depression Clinical and Research Program (DCRP), or the Center for Addiction Medicine (CAM) at MGH. Study staff may walk participants between ARMS and the DCRP or CAM as needed.

In sum, the proposed study involves the following points of contact: (1) obtaining informed consent and screening/baseline assessment, (2) mid-treatment assessment involving self-report questionnaires and TLFB, (3) post-treatment assessment involving self-report questionnaires and TLFB (primary endpoint), and (4) 16 twice-weekly group UP sessions for those randomized to the UP + TAU condition.

If participants are unable to complete the clinician-rated measures in-person at their mid- or post-treatment assessments, they will be given the option to complete this portion of the visit via phone call with a study clinician. Should any risk issues arise, the clinician will complete a risk assessment while on the phone with the participant. A licensed clinician will always be on-site for consultation as needed during assessments conducted over the phone.

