Patient Health Questionnaire (PHQ-9⁶³): A nine-item measure of depressive symptoms. It will be administered at each of the three assessment points to participants in both conditions.

Generalized Anxiety Disorder Assessment ($GAD-7^{64}$): A 7-item measure of generalized anxiety symptoms. It will be administered at each of the three assessment points to participants in both conditions.

Short Version of the UPPS-P Impulsive Behavioral Scale (SUPPS-P⁶⁵): A 20-item version of the original UPPS-P Impulsive Behavior Scale that assess five distinct facets of impulsivity: negative urgency, sensation seeking, lack of premeditation, lack of perseverance, and positive

urgency. It will be administered at each of the three assessment points to participants in both conditions.

*Emotion Reactivity Scale (ERS*⁶⁶): A 21-item self-report measure of emotion sensitivity, intensity, and persistence. It will be administered at each of the three assessment points to participants in both conditions.

Drug Use Motives Questionnaire (DUMQ^{67, 68}): An adapted version of the original Drug Use Motives Questionnaire; a 17-item measure to assess reasons or motives for using substances. It will be administered at the screening/baseline visit only.

Concomitant Treatment Log: A log that captures overall treatment plan, including therapy and medication, as well as the corresponding start and stop dates for each treatment. A study clinician will complete the log at the screening/baseline visit, and update the log at the mid- and post-treatment assessment visits.

Study clinicians and subjects will complete all measures on paper copies. Data collected will then be entered directly into REDCap by study staff.

Table 1 (below) outlines the schedule of assessments for the study.

Table 1. Schedule of Assessments

Assessment	Screen /Baseli ne	Week 1	Week 2	Week 3	Week 4 / Mid- treatment	Week 5	Week 6	Week 7	Week 8 / Post- treatment
Informed Consent	X								
Form									
Demographics/	X								
Contact Info Inclusion/	X								
Exclusion	X								
Adverse Events					X				X
Tracking Form					Λ				Λ
Concomitant	X				X				X
Treatment Log									
PHQ-9	X				X				X
GAD-7	X				X				X
SUPPS-P	X				X				X
ERS	X				X				X
DUMQ	X								
SITBI-CR	X								
SITBI-SR					X				X
BSI	X				X				X
CSS	X				X				X
Craving Scale	X				X				X
TLFB	X				X				X
ERQ	X				X				X
BEAQ	X				X				X
OASIS	X	X (UP +	X (UP +	X (UP +	X	X (UP +	X (UP +	X (UP +	X

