		TAU only)	TAU only)	TAU only)		TAU only)	TAU only)	TAU only)	
ODSIS	X	X (UP +	X (UP +	X (UP +	X	X (UP +	X (UP +	X (UP +	X
GGO 0 1		TAU only)	TAU only)	TAU only)		TAU only)	TAU only)	TAU only)	W (LID :
CSQ-8 and Feedback Interview									X (UP + TAU only)
Approximate Time Estimate	< 60 min	< 5 min	< 5 min	< 5 min	45 to min	< 5 min	< 5 min	< 5 min	45 (TAU) to 60 min (UP+TAU)

Study Intervention

Study Therapists and Training: Masters- or doctoral-level clinicians at ARMS and/or the DCRP will deliver the UP treatment. One to two therapists will (co-)lead each group session. All study therapists will be trained in the protocol by [name] (co-investigator), who has been extensively trained and certified in delivering the UP by a treatment developer. Study therapists will meet weekly with [name] (ARMS Clinical Director) for clinical supervision, or more frequently as needed. A licensed clinician will be on-site at ARMS and available for consultation and risk management as needed whenever a UP group is conducted. Consistent with routine clinical practice at ARMS, should a participant present with clear alcohol or drug intoxication or spontaneously disclose suicidal or homicidal ideation during a UP group session, a study clinician will meet individually with the participant for a clinical risk assessment. If needed, a transfer to the MGH emergency room will be facilitated immediately.

Treatment Fidelity: Recommendations suggested by the NIH Behavior Change Consortium workgroup on treatment fidelity will be implemented. Therapists will be trained on the UP treatment, and adherence to the manual will be monitored. Group sessions will be audio-recorded in order to facilitate supervision and manual adherence. A random selection of audiotapes will be rated for adherence using scales adapted from a previous, large-scale grant-funded UP trial⁴⁰. Study therapists will meet at least monthly to discuss adherence to the protocol, or more frequently as needed.

Description of the UP Treatment

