General safeguards consistent with good clinical practice will be in place for all subjects enrolled in the study. As part of routine clinical care at ARMS, all subjects will have an ARMS clinician contact who they can access by pager 24 hours a day, 7 days per week for emergencies. During the informed consent process and as needed throughout the study, subjects will be encouraged to page their ARMS clinician contact in the event of a crisis. As part of the MGH, all research subjects can access the Acute Psychiatry Service in the emergency room at any time of the day or night. The PI will be responsible for monitoring the safety of the study and complying with the reporting requirements. Continuous, close monitoring of participant safety will include prompt and frequent reporting of safety data (i.e., adverse/serious adverse events) to the MGH IRB and/or appropriate study staff with oversight responsibility. Serious adverse events (SAEs) will be reported to the Data Safety and Monitoring Board (DSMB) members. SAEs will also be reviewed by the PI every 6 months during progress reports as well as during the written report required by the IRB as part of the annual IRB renewal process.

Data Safety and Monitoring Board (DSMB): A DSMB will be assembled prior to the start of the study. This will consist of three independent staff-level investigators; one will have expertise in clinical interventions with individuals with SUD; the second will have expertise in clinical trial design; the third will have expertise in biostatistical analysis. The DSMB will meet every six months during the study to review progress, address any difficulties with recruitment, and address any safety related matters that may arise. The DSMB will be provided with unblinded data from the study so as to determine whether that risk to subjects outweighs the potential benefits. If at any time during the course of the study, the DSMB judges that risk to subjects outweighs the potential benefits, the DSMB shall have the discretion and responsibility to recommend that the study be terminated. In addition to the IRB, all DSMB members will be informed of any serious adverse events occurring during the study.

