Adverse Event Reporting: Consistent with good clinical practice, safety will be closely monitored by study staff. The PI will oversee all study activities including self-report and clinician ratings. All procedures have been designed to minimize subject discomfort, and no subject will be asked to engage in research procedures not outlined in the consent form. Subjects will be monitored for adverse events at each assessment visit by a study clinician. All adverse events (including unexpected and serious AEs) will be recorded and reported in accordance with Partners HealthCare guidelines. A subject may be dropped from the study at any time due to adverse events. We will follow and adhere to all guidelines as defined and outlined on the Partners Human Research Committee web site:

http://healthcare.partners.org/phsirb/adverse.htm. The PI will be responsible for ensuring that adverse events are reported to the local IRB in compliance with local and federal requirements. Any changes to the protocol will be made in accordance with MGH IRB policies.

Data Monitoring: The PI will be responsible for ongoing quality control, including data integrity and protocol compliance. All clinician-rated data will be collected on paper and entered into Redcap. All self-report data that is collected on paper will be entered into Redcap. If a participant is unable to complete self-report measures in person, the data will be entered directly into Redcap remotely by the participant. To ensure usability of self-report data, a member of study staff (whoever is conducting the assessment) will review all self-report measures within one week of submission to insure their completeness. All self-report assessment forms and clinician-administered instruments will be reviewed by study staff within one week of their completion to assure that they are being completed correctly. Any errors in completion will be reviewed to determine if directions or procedures for the assessments need to be altered. In this case, permission from the IRB will be requested to change any procedure. The group sessions will also be audiotaped (with subjects' permission) and a random selection will be rated for competence and adherence to the protocol. This will also ensure the usability of the data.

Confidentiality:

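### Adverse events are actively sought only at two assessments, with no stated ascertainment after dropout and unequal detection and observation time by arm, so the safety data may be incomplete and not comparable

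*Protocol*

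**What the plan says.** **Scheduled elicitation.** Protocol section IX, Adverse Event Reporting: "Subjects will be monitored for adverse events at each assessment visit by a study clinician". In Table 1 the row beginning "Adverse Events" is marked at mid-treatment and post-treatment only, with no restriction by arm. The same part of section IX adds: "All adverse events (including unexpected and serious AEs) will be recorded and reported in accordance with Partners HealthCare guidelines".

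**Further study contacts in one arm.** Under section V, participants allocated to UP + TAU will "be offered 16 additional, twice-weekly group UP sessions". The Study Intervention part sets out what happens "should a participant present with clear alcohol or drug intoxication or spontaneously disclose suicidal or homicidal ideation during a UP group session". The response it gives is an individual risk assessment by study staff. Section IX, Safety Monitoring, names assessment visits and UP sessions as the places where intoxication is handled, and does not mention TAU sessions. OASIS and ODSIS are completed at every UP session.

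**Timing of the last assessment.** Section V places the TAU post-treatment assessment 8 to 10 weeks after randomization. The UP + TAU one falls within two weeks after the participant's 16th UP session. The description of the UP treatment allows a wait of up to 4 weeks before the first session for a group randomized during UP Weeks 6 to 8.

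**End of follow-up.** Under section V, a participant who leaves three consecutive contact attempts unanswered within three weeks counts as dropped out and is not followed further. Section IX also drops participants whose mental health makes outpatient treatment unsuitable.

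**Use of the data.** Section IX: "The DSMB will be provided with unblinded data from the study so as to determine whether that risk to subjects outweighs the potential benefits". Consent to record access and data exchange with ARMS is compulsory. Its stated purposes include confirming eligibility, extracting clinical data, and to "track treatment engagement at ARMS, and facilitate good clinical care during the study". Adverse event capture is not named.

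**The concern.** Three features bear on the safety data.

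1. Events are actively asked about at two assessments. A participant who is hospitalised, overdoses or disappears before an assessment may leave no adverse event data, and nothing in the document says how that gap is filled.
2. Because all adverse events are to be recorded, anything study therapists learn at UP sessions can enter the study record. No written procedure brings an event seen at a TAU session into that record.
3. The period covered by the last assessment can be longer in UP + TAU.

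The DSMB may recommend stopping the study on its judgement of risk against benefit. The protocol expects continued substance use during outpatient care, so the TAU arm is the natural reference for separating background events from harm caused by the intervention. If events are counted differently in the two arms, that reference is weakened. Events never collected cannot be recovered at the analysis stage.

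**Working it through.** The protocol gives no adverse event rate, capture rate or safety-comparison figure, so there is no stated number to reproduce.

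**Step 1: contacts (section V, Table 1).**
- Scheduled adverse event points: 2 in TAU and 2 in UP + TAU.
- Further UP sessions: 0 in TAU and up to 16 in UP + TAU.

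**Step 2: time to the post-treatment assessment.**
- TAU: 8 to 10 weeks from randomization.
- UP + TAU without a wait: 8 weeks of sessions plus up to 2 weeks, so about 8 to 10 weeks. The arms agree.
- UP + TAU with the longest stated wait: 4 + 8 + 2 = 14 weeks, assuming no delay within the 16 sessions.
- Ratio of windows at that maximum: 14/10 = 1.4 to 14/8 = 1.75.

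The ratio applies to participants who wait the full 4 weeks, not to the arm average. The protocol also allows a wait when too few participants are enrolled to form a group, and states no limit for it.

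**Step 3: illustration of unequal detection.** All inputs are assumptions. Let r be the true event risk, equal in both arms. Let s be the share of events captured at assessments, equal in both arms. Let x be the share of the remaining events that comes to light only through UP sessions.

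- Recorded risk in TAU = r × s
- Recorded risk in UP + TAU = r × (s + (1 − s) × x)
- Apparent risk ratio = 1 + x(1 − s)/s
- Absolute excess = r × (1 − s) × x

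| s | x | Apparent risk ratio | Excess at r = 0.2 | Excess at r = 0.4 |
|---|---|---|---|---|
| any | 0 | 1.00 | 0 | 0 |
| 0.9 | 0.5 | 1.06 | 1 point | 2 points |
| 0.8 | 0.25 | 1.06 | 1 point | 2 points |
| 0.8 | 0.5 | 1.12 | 2 points | 4 points |
| 0.6 | 0.25 | 1.17 | 2 points | 4 points |
| 0.6 | 0.5 | 1.33 | 4 points | 8 points |

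For the last row at r = 0.2, recorded risk is 0.2 × 0.6 = 12% in TAU and 0.2 × (0.6 + 0.4 × 0.5) = 16% in UP + TAU. Across s = 0.6 to 0.9 and x = 0 to 0.5, the ratio runs from 1.00 to 1.33 and the excess from 0 to 8 points. This covers detection only; the longer window in Step 2 would add to it.

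**Step 4: loss to follow-up.** The dropout rule is the same in both arms, so it makes the data incomplete in both. It distorts the comparison only if dropout differs. Hypothesis 1b predicts less dropout from ARMS treatment in the UP arm. If study dropout follows that pattern, more TAU events go unseen, in the same direction as Step 3.

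**The case against.** The strongest reply is that the plan treats the arms alike where it matters. The adverse event form has the same schedule in both, and BSI, SITBI-SR, TLFB and the concomitant treatment log are collected in both at the same two assessments. This stands: the asymmetry lies in opportunistic detection and window length, not in scheduled elicitation.

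A reader might go further and infer any of the following. The document does not support them.

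- **Events count only if the participant attends.** Clinician-rated parts can be done by phone, self-report can be completed remotely, a missed mid-treatment visit does not bar the post-treatment one, and all adverse events are to be recorded whatever their source.
- **A TAU event reaches the study only through a later visit.** ARMS clinicians may be study staff, the ARMS Clinical Director supervises the study therapists, and data exchange with ARMS is compulsory. The route is unwritten for adverse events, but it is not excluded. A contrast of 18 contacts against 2 ignores this overlap.
- **The apparent risk in UP + TAU would double.** That needs full capture in one arm and half in the other, which nothing in the document supports.
- **The DSMB works from a biased comparison.** No between-arm adverse event analysis is specified, and the members, who include trial-design and biostatistics expertise, receive unblinded data.

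It is also fair that the protocol does not classify intoxication or disclosed ideation as adverse events and refers to institutional guidelines not shown here. How many UP-session observations would be recorded as events is therefore unknown.

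These points limit the size of the problem. They do not supply ascertainment after dropout, a TAU counterpart to UP-session detection, or a common observation window.

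**Conclusion.** The concern holds as a risk of incomplete and non-comparable safety data, not as a demonstrated bias. Three gaps follow from the text: active elicitation at two assessments only, no described ascertainment for participants who become unresponsive or are dropped, and study-staff detection and a possibly longer window in UP + TAU. The likely direction is toward more recorded events in UP + TAU. The size cannot be fixed from the document. The risk ratio of 1.00 to 1.33 rests on assumed capture rates and equal true risk, and the 14-week window on the maximum stated wait with no delay in the sessions. The change is worth making because the access it needs is already consented and the data cannot be recovered later.

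**What to change.** In section IX, Adverse Event Reporting, and in Table 1:

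1. Add a check of the medical record and ARMS data for adverse and serious adverse events (for example hospitalisation, emergency visit, suicide attempt, overdose) for every randomized participant, including those who drop out or miss visits.
2. Cover one common calendar interval from randomization in both arms, instead of ending at each participant's own post-treatment visit.
3. Record on the form how each event was found: assessment, record or ARMS check, or UP session.
4. Give the DSMB all events. Show between-arm counts from the common sources and interval alongside the full list, so that events found only at UP sessions remain visible and possible harms of the group are not set aside.

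The cost is one look-up per participant by staff who already track ARMS attendance, plus wording in the protocol and on the form. The recorded event count will rise. The consent text on record use may need a change; the consent form is not available here, so this could not be checked. No clinical rule changes.
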